### Ethical Approval

For the implementation of the research, Ministry of Health, Provincial Health Directorate, Health Sciences University, Abdurrahman Yurtaslan received approval from Ankara Oncology Training and Research Hospital, Health Practice and Research Center Clinical Research Ethics Committee (decision no: 2019-02 / 218)

## **Ethical Consideration**

Written permission and approval was obtained from the Oncology Training and Research Hospital, Health Practice and Research Center Clinical Research Ethics Committee before the study started (decision no: 2019-02 / 218). Surgeon and operating room nurses within Gülhane Training and Research Hospital were informed of the study and verbal approval was obtained.

## **Statistical Analysis**

The data obtained from this study were evaluated by using the Statistical Package for the Social Sciences (SPSS, Inc., Chicago, IL, USA) 22.0 software program. After the data were transferred to the SPSS database, error controls were performed. Their compliance with a normal distribution was evaluated with Kolmogorov Smirnov test. The data determined were mean  $\pm$  standard deviation ( $X \pm SS$ ), median and minimum-maximum (min-max) for the variables determined by the measurement and number (n) and percent (%) for the variables determined by counting. Since the variables determined by counting did not comply with a normal distribution, the difference between the four groups was evaluated by the Chi square test. The one-way ANOVA test was used to investigate the difference between the four groups regarding the measured values for values complying with normal distribution and the Kruskal-Wallis test was used for the values that did not comply with a normal distribution. The Bonferroni correction was implemented to determine the source of the difference in group comparisons. In the comparison of four measurements within the group, the "Friedman Test" was used for data that did not conform to normal distribution. In order to understand from which measurement the difference arises, "Wilcoxon Test with Bonferroni Correction" was used as Post Hoc Test. The Mann-Whitney U test was used to investigate the difference between two groups of variables. A p value  $<0.05$  was accepted as statistically significant.

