### **Hypothesis**

#### 1. Method

H0: There is no difference between the effectiveness of different surgical hand scrubbing methods on the bacterial flora in the hand

H1: There is a difference between the effectiveness of different surgical hand scrubbing methods on the bacterial flora in the hand.

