#### 2. Time

H0: There is no difference between the effectiveness of different the duration of scrubbing time on the bacterial flora in the hand.

H1: There is a difference between the effectiveness of different the duration of scrubbing time on the bacterial flora in the hand.

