### **Sample Size**

The sample size is at least 180 people for one-way analysis of variance with G \* Power version 3.1.19 software to determine a medium level (0.25) effect size between 4 groups at 0.80 power and 0.05 type I error level calculated (Tsai, 2016). Participants will be divided into 4 groups by randomization method.

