## **Randomization**

- ✓ Group I: The participants in the first group performed the surgical hand scrubbing for 1 minute and with using nail brush (n=45).
- ✓ Group II: The participants in the second group performed the surgical hand scrubbing for 1 minute and without using a nail brush (n=45).
- ✓ Group III: The participants in the third group performed the surgical hand scrubbing for 2 minute and with using nail brush (n=45).
- ✓ Group IV: The participants in the fourth group performed the surgical hand scrubbing for 2 minute and without using a nail brush (n=45).

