### *Scrubbing Stage*

Group I: Surgical hand scrubbing group using a brush (only nails) (Total scrubbing time 1 min)

1. The bottom of the nails is cleaned under running water with a disposable nail brush (30 seconds).
2. Hands and forearms are washed by scrubbing them towards the elbow for 30 seconds with the help of 3ml antiseptic solution.
3. Hands and forearms are thoroughly rinsed under running water.
4. Hands and forearms are washed by scrubbing them towards the elbow for 30 seconds again with the help of 3 ml antiseptic solution.
5. Hands and forearms are rinsed thoroughly under running water.

Group II: Surgical hand scrubbing group (Control group) without brush (Total scrubbing time 2 min)

1. Hands and forearms are washed by scrubbing towards the elbow for 30 seconds with the help of 3 ml antiseptic solution.
2. Hands and forearms are thoroughly rinsed under running water.
3. Hands and forearms are washed by scrubbing them towards the elbow for 30 seconds again with the help of 3 ml antiseptic solution.
4. Hands and forearms are rinsed thoroughly under running water.

Group III: Surgical hand scrubbing group using a brush (only nails) (Total scrubbing time total 2 minutes)

Applications made in Group I are applied in the same way as scrubbing for 2 minute.

Group IV: Surgical hand scrubbing group (Control group) without brush (Total scrubbing time 2 minutes)

Applications made in Group IV are applied in the same way as scrubbing for 2 minute.

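### Hypothesis 2 (scrub time) has no identified deciding test, because a crossed brush-by-time design is analysed as four unstructured groups

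*Combined protocol and SAP*

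**What the plan says.** The Hypothesis section has two parts, each with its own null. The alternative under 1. Method is "There is a difference between the effectiveness of different surgical hand scrubbing methods on the bacterial flora in the hand". The alternative under 2. Time is "There is a difference between the effectiveness of different the duration of scrubbing time on the bacterial flora in the hand".

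The Randomization section lists four arms of 45: brush and no brush at 1 minute, brush and no brush at 2 minutes. This is a 2x2 layout, with 90 v 90 on each factor.

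The Sample Size section arrives at 180 for a one-way ANOVA "to determine a medium level (0.25) effect size between 4 groups at 0.80 power and 0.05 type I error level". It gives no power for brush or for time.

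The Statistical Analysis section says "The one-way ANOVA test was used to investigate the difference between the four groups regarding the measured values" where the data are normal, with Kruskal-Wallis otherwise. It then names two follow-up steps: "The Bonferroni correction was implemented to determine the source of the difference in group comparisons" and "The Mann-Whitney U test was used to investigate the difference between two groups of variables". It does not list the pairs, say how many there are, or identify the two groups. It names no two-way model, no interaction test and no baseline adjustment, although the Data Collection section provides a pre-scrub culture.

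**The concern.** A significant four-group test says that some arms differ. It does not say whether time, brush or a single arm is responsible, so it cannot decide Hypothesis 2. That decision could rest on the 1 v 2 minute comparison with a brush, on the one without a brush, or on all 90 v 90. These can disagree, and the plan does not say which governs.

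Two errors of reading become possible. A non-significant 45 v 45 pair may be taken to show that time makes no difference. And whichever comparison happens to be significant may be presented afterwards as the test of the hypothesis.

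The time factor itself also needs settling before it can be coded. For Group II the Randomization section says "The participants in the second group performed the surgical hand scrubbing for 1 minute and without using a nail brush (n=45", while the Scrubbing Stage section says "Group II: Surgical hand scrubbing group (Control group) without brush (Total scrubbing time 2 min", and the steps listed there add to 2 × 30 = 60 s. Group IV is described there by reference to itself.

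**Working it through.** **Inputs from the documents:** N = 180, four cells of 45, f = 0.25, alpha 0.05.

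**Assumptions:** roughly normal data, no losses, and the planned f = 0.25 spread over the four cells in one of three patterns.

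**1. The plan's own figure.** Power is the probability that a noncentral F with df1 and N − 4 degrees of freedom and noncentrality λ = N·f² exceeds its critical value. With df1 = 3 and df2 = 176, λ = 180 × 0.25² = 11.25 and power is 0.804. The figure of 180 is reproduced.

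**2. Three patterns with overall f = 0.25.** A time effect of d SD between the two 90-person halves has f = d/2.
- (a) Only time acts: d = 0.5, f = 0.25, λ = 11.25.
- (b) Brush and time act equally: f = 0.25/√2 = 0.177 each, d = 0.354, λ = 5.625.
- (c) One cell is shifted by δ: overall f = δ√3/4 = 0.25, so δ = 0.577 SD. Averaged over brush, the time effect is δ/2, so f = 0.25/√3 = 0.144 and λ = 3.75.

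**3. Time main effect** (df1 = 1, df2 = 176). Two tests at 0.05 each have a family-wise error of about 1 − 0.95² = 0.0975 (0.097 by simulation). At 0.025 each it is about 0.05, which is the fair comparison with Bonferroni pairs.

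**4. Bonferroni pairs.** Groups I v III and II v IV isolate time. Six pairs are tested at 0.05/6 = 0.0083, four at 0.05/4 = 0.0125. Time is credited if the four-group test and either time pair are significant (pooled error, 40,000 simulated trials per pattern).

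| Pattern | Main effect, 0.025 | Main effect, 0.05 | Six pairs | Four pairs |
|---|---|---|---|---|
| (a) only time acts | 0.862 | 0.916 | 0.617 | 0.676 |
| (b) both act equally | 0.545 | 0.655 | 0.301 | 0.362 |
| (c) one cell differs | 0.375 | 0.486 | 0.531 | 0.581 |

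Hand check for six pairs: the power of one pair is about Φ(d√(45/2) − 2.638).
- (a) Φ(2.372 − 2.638) = 0.395; at least one of two independent pairs, 1 − 0.605² = 0.634.
- (b) Φ(1.677 − 2.638) = 0.168; 1 − 0.832² = 0.308.
- (c) Only one time pair carries the effect: Φ(2.739 − 2.638) = 0.540.

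These treat the SD as known, so they sit slightly above the simulation.

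In pattern (b), about a third (four pairs) to two fifths (six pairs) of significant four-group tests come with no significant pair that isolates either factor.

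**5. If Mann-Whitney means 90 v 90.** At 0.05, simulated power for time is 0.902, 0.626 and 0.453 in (a), (b) and (c). Against 0.916, 0.655 and 0.486 the loss is 0.014, 0.029 and 0.033.

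**6. Interaction.** If the time effect differs by 0.5 SD with and without a brush, f = 0.5/4 = 0.125, λ = 180 × 0.125² = 2.81 and power is 0.385, unadjusted.

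**7. Pre-scrub covariate.** Divide f by √(1 − r²), with df2 = 175. The documents give no correlation. For an assumed r of 0.3, 0.5 or 0.7, main-effect power in (b) at 0.05 is 0.696, 0.777 or 0.910.

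**The case against.** The best defence is that tests of both factors do exist. The Bonferroni sentence follows the four-group tests directly, and its ordinary reading is all pairwise comparisons. Those include I v III and II v IV for time, and I v II and III v IV for brush. The Scrubbing Stage section calls both no-brush arms control groups, which points to the brush comparisons. Mann-Whitney may simply be the pairwise follow-up to Kruskal-Wallis. A reader might infer that neither factor is tested at all; the documents do not support that. What stands is that the comparisons are unnamed, that each uses 45 v 45, and that none is designated to decide Hypothesis 2.

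The Mann-Whitney sentence could also mean brush v no brush or 1 v 2 minutes at 90 v 90, in which case the power loss nearly vanishes. It could equally mean surgeon v nurse. The text does not settle this.

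If methods in Hypothesis 1 means the four regimens, the four-group test does answer it. That reading leaves Hypothesis 2 open.

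It is tempting to set 0.916 against the pairs. That compares 0.05 per factor with pairs held at about 0.05 overall; 0.862 is the matched figure. It is also tempting to call the missing interaction test a contradiction. No interaction hypothesis is stated, so its absence is a secondary gap.

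**Conclusion.** The concern holds as a gap in specification that should be fixed. Hypothesis 2 has no identified deciding test, and Hypothesis 1 shares the gap if methods means brush use.

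The size depends on the route intended. If it is pairs, the matched loss of power to credit time is about 0.18–0.24 when only time acts (0.862 less 0.68 or 0.62) and 0.19–0.24 when both factors act equally (0.545 less 0.36 or 0.30). When one cell differs, the pairs do better. If it is 90 v 90 Mann-Whitney tests, the loss is about 0.01–0.03 and the gap is mainly one of labelling and baseline adjustment. All of this assumes roughly normal data and no losses, although the plan allows for skewed data and lists reasons for withdrawal.

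A reader might infer that 180 is too few or that the four-group test has inflated type I error. Neither follows: 180 is correct for that test, and its error level is not affected.

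**What to change.** First reconcile the Randomization and Scrubbing Stage sections on Group II's total time and Group IV's self-reference, against what was done. Then:

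- Fit a two-way model (brush, time, brush × time) of log10 CFU at one stated post-scrub stage, with pre-scrub log10 CFU as covariate. State a rule for zero counts and a rank-based fallback if zeros are common, for example the same model on ranks.
- Decide Hypothesis 2 by the time main effect and Hypothesis 1 by the brush main effect. If methods means the four regimens, say so and keep the four-group test for Hypothesis 1.
- Test at 0.025 each, or at 0.05 each with the family-wise error of about 0.097 stated. Give estimates with 95% confidence intervals.
- Report the interaction and simple effects as secondary, with the low interaction power acknowledged. Keep the four-group comparison.
- Name the Bonferroni pairs and their number, and say which two groups the Mann-Whitney test compares.
- Label the model post hoc if the data have already been analysed; the Study Setting and Statistical Analysis sections are written in the past tense.

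The cost is SAP wording and one model in the same software on data already collected. The downsides are less power than pairs for a single-cell effect, little power for the interaction, the need for a zero-count rule, and a probable post hoc label.

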### **Study Setting**

This study was conducted at the Department of Operating Room of the Gülhane Training and Research Hospital in Ankara, Turkey between November 2019 and April 2020.

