### **Method and Participants**

The research is a randomized controlled prospective study. The universe of the research will be surgeon and operating room nurses in Gülhane Training and Research Hospital.

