## **Data Collection**

This research will take place in three stages. At all stages (before surgical hand scrubbing, immediately after and at the end of the surgery), culture will be taken from the active hands of the participants with the Glove Juice Method. At all stages, culture will be taken from the participants via Glove Juice Method.

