### *Applications in Medical Microbiology Laboratory*

Before surgical hand scrubbing, samples taken with glove liquid technique were diluted 1:10 in Müller Hinton Broth broth in the laboratory (500  $\mu$ l sample, 4.5 ml. Müller Hinton Broth). And 300  $\mu$ l of it was placed on 5% sheep blood agar plates with sterile micropipettes. 1 ml each of the other samples (after surgical hand scrubbing and at the end of the surgery) was spread diluted into three 5 % sheep blood agar plates with sterile micropipettes. All samples were incubated at 35° C for 48 hours under atmospheric conditions. Total bacterial load was determined by counting the total colony forming units (CFU) on the plates.

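### The between-arm tests leave out the pre-scrub count already collected and do not define the quantity compared; they stay valid but give up precision of unknown size

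*Combined protocol and SAP*

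**What the plan says.** The Method and Participants section describes the design: "The research is a randomized controlled prospective study". The Randomization section allocates 45 people to each of four arms. The Data Collection section sets three sampling times: "At all stages (before surgical hand scrubbing, immediately after and at the end of the surgery), culture will be taken". Every participant therefore has a baseline measurement of the outcome itself.

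The laboratory section treats the samples differently. The pre-scrub "samples taken with glove liquid technique were diluted 1:10 in" broth, and 0.3 ml of the dilution was plated. For the rest, "1 ml each of the other samples (after surgical hand scrubbing and at the end of the surgery) was spread diluted" over three plates. Load is then determined by counting colonies, and no conversion to a common unit is given.

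For the comparison of arms, the Statistical Analysis section states: "The one-way ANOVA test was used to investigate the difference between the four groups regarding the measured values". Kruskal-Wallis replaces ANOVA when normality fails, Bonferroni correction is used to locate differences, and Mann-Whitney handles two-group comparisons. No covariate, transformation, change score or time point is named. The repeated samples are combined only in the Friedman and Wilcoxon tests, introduced with "In the comparison of four measurements within the group" (four, although only three sampling times are described). The Sample Size section rests on the same unadjusted test: "The sample size is at least 180 people for one-way analysis of variance".

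**The concern.** Two things are missing from the between-arm analysis.

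- **No use of baseline.** People differ in the bacterial load they start with. If that difference carries over into the later counts, it stays in the error term even though it was measured. The Friedman and Wilcoxon tests do use the pre-scrub count, but only within an arm, so they do not address either hypothesis about differences between methods or durations.
- **No defined quantity.** The values compared could be raw counts, log counts or reductions from baseline, at either later sample. These choices have different power. A reduction computed from raw colony numbers would also mix two plating scales.

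At stake are the width of the confidence intervals and the chance of detecting a real difference. The validity of the tests is not in question on this point.

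**Working it through.** **Inputs.** From the Sample Size and Randomization sections: four arms, 45 each, N = 180, f = 0.25, alpha 0.05, target power 0.80. The correlation r between pre-scrub and later log10 counts is not given, so I take 0 to 0.7 as an assumed range.

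**1. The plan's own figure.** For one-way ANOVA the noncentrality is λ = N f² = 180 × 0.0625 = 11.25, with 3 and 176 degrees of freedom. Power is 0.804. N = 176 gives 0.794, so 180 is the smallest equal-group total and the stated figure reproduces.

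**2. Validity without adjustment.** In 10,000 simulated null trials at each of r = 0, 0.5 and 0.7, type I error was 4.7%, 5.0% and 4.9% for ANOVA, and 4.6%, 5.0% and 4.7% for Kruskal-Wallis.

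**3. Baseline adjustment.** ANCOVA multiplies the error variance by 1 − r² and uses one degree of freedom: λ = 11.25/(1 − r²), with 3 and 175 degrees of freedom. The equivalent unadjusted N is 180/(1 − r²), and confidence intervals narrow by 1 − √(1 − r²).

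**4. Change score.** With equal log10 SDs before and after, the variance factor is 2 − 2r: λ = 11.25/(2 − 2r), with 3 and 176 degrees of freedom.

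| r | λ, ANCOVA | Power, ANCOVA | Equivalent N | CI narrower by | λ, change | Power, change |
|---|---|---|---|---|---|---|
| 0 | 11.25 | 0.804 | 180 | 0% | 5.63 | 0.48 |
| 0.2 | 11.72 | 0.821 | 188 | 2% | 7.03 | 0.58 |
| 0.3 | 12.36 | 0.843 | 198 | 5% | 8.04 | 0.65 |
| 0.5 | 15.00 | 0.911 | 240 | 13% | 11.25 | 0.80 |
| 0.7 | 22.06 | 0.983 | 353 | 29% | 18.75 | 0.96 |

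The change score beats the plain later count only if 2 − 2r < 1, that is r > 0.5. Since (2 − 2r) − (1 − r²) = (1 − r)² ≥ 0, its error variance is never below that of ANCOVA.

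**5. Plating scales.** Before scrubbing, 0.3 ml of a 1:10 dilution carries 0.03 ml of the original fluid. One colony therefore stands for 50/0.03 ≈ 1,667 CFU per 50 ml glove. For the later samples, reading the text as 1 ml in total over three plates, one colony stands for 50/1 = 50 CFU. The gap is log10(1,667/50) = 1.52. If 1 ml went on each plate, the later factor is 50/3 ≈ 17 and the gap is 2.00.

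**6. Realistic plate counts.** The table assumes normal outcomes. A simulation with Poisson plate counts on the step 5 volumes used assumed log10 means of 4.5 before and 2.0 after, SD 0.6 and a half-colony offset. About 25% of post-scrub counts were zero. None of these means or SDs comes from the documents. ANCOVA on log counts held its type I error (0.043 to 0.051). Power, unadjusted ANOVA on log counts against ANCOVA, was:

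- r = 0: 0.68 and 0.68
- r = 0.3: 0.68 and 0.70
- r = 0.5: 0.68 and 0.77
- r = 0.7: 0.68 and 0.86

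A repeat of 1,000 runs gave 0.66 and 0.73 at r = 0.5, so the second decimal is not firm. Plating noise and zeros reduce the observed r from 0.3, 0.5 and 0.7 to about 0.25, 0.42 and 0.59, which is why these gains are smaller than in the table.

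**The case against.** The strongest reply is that this is a preference for efficiency. The trial was sized for an unadjusted ANOVA, that calculation reproduces, and the plan meets its own power target without a covariate. With r unknown the gain may be nil, and with many zero counts it is smaller than textbook figures suggest. All of this stands, and it is why the point concerns precision and not error.

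Three further replies have partial force.

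- The plan never names a change score. That is true, but it does not exclude one either, and the cost of that reading at low r is a reason to define the quantity.
- The plating factor is the same in every arm. It cancels in a comparison at one time point and, apart from the zero offset, is absorbed by the intercept on the log scale. This is correct: it harms raw change scores and the within-arm tests, not a comparison of arms on later counts alone. The 1.52 log10 gap is also only one reading of the laboratory text.
- The tests have other weaknesses, such as stopping data collection after glove damage, a four-arm omnibus test for two separate hypotheses, and no stated primary time point. These are real but separate. They limit the statement that the tests stay valid to the missing covariate alone.

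None of this removes the core point: a baseline of the outcome is available, adjusting for it costs almost nothing even at r = 0, and the analysed quantity is not stated.

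**Conclusion.** The concern holds. The between-arm tests ignore a baseline that every participant provides, and the plan does not define what is compared. Omitting the baseline does not invalidate the tests under randomisation.

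Under the plan's own N and effect size, the power given up is nil at r = 0, about 0.04 at r = 0.3, 0.11 at r = 0.5 and 0.18 at r = 0.7. In the zero-heavy simulation the corresponding gains are 0, 0.02, 0.09 and 0.18. The correlation may also be lower at the end of surgery than just after scrubbing. If the undefined quantity is a change from baseline and r is below 0.5, power falls below the stated 0.80.

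These figures assume a roughly linear relation on the log10 scale with common variance and, for the change score, equal SDs before and after. Because r is not in the documents, no single figure for the loss can be given. The change should be made, but the trial does not fail without it.

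**What to change.** In the Statistical Analysis section:

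- State the analysed quantity and convert every count to CFU per hand from the plated volume and dilution. First clarify whether the later samples used 1 ml in total or 1 ml per plate, and whether they were diluted further.
- Compare arms at each of the two later samples by ANCOVA on log10 CFU, with the participant's own log10 pre-scrub count as covariate. Report adjusted differences with 95% confidence intervals.
- Do not use a raw change score.
- Keep Kruskal-Wallis as a sensitivity analysis, and treat the within-arm Friedman and Wilcoxon tests as descriptive.
- Fix an offset for zero counts, for example half a colony, and check how results vary with its value.

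The choice of a primary time point and the handling of multiplicity remain to be settled separately.

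The cost is wording, one degree of freedom and the offset check, with no new data. One caution applies. The Study Setting section dates the conduct "between November 2019 and April 2020", and the statistical section reports in the past tense that some variables were not normal. If the data had been examined before the change, the adjusted analysis must be labelled post hoc and shown beside the planned one. Defining the outcome and converting the units remain useful for reporting either way.

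### One-way ANOVA is conditional on normality alone, with no unequal-variance version: if colony counts take that route with a pooled error and scrub time shrinks their spread, the 2-minute brush comparison loses power

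*Combined protocol and SAP*

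**What the plan says.** The outcome is a bacterial count (Applications in Medical Microbiology Laboratory): "Total bacterial load was determined by counting the total colony forming units (CFU) on the plates". The Sample Size section plans for ANOVA: "The sample size is at least 180 people for one-way analysis of variance", with the target "to determine a medium level (0.25) effect size between 4 groups at 0.80 power and 0.05 type I error level calculated". The Randomization section crosses brush (yes or no) with time (1 or 2 minutes), 45 people per arm.

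The Statistical Analysis section chooses the test for measured variables from one check: "Their compliance with a normal distribution was evaluated with Kolmogorov Smirnov test". If a variable passes, "The one-way ANOVA test was used to investigate the difference between the four groups regarding the measured values for values complying with normal distribution". If it fails, "the Kruskal-Wallis test was used for the values that did not comply with a normal distribution". For follow-ups the text says "The Bonferroni correction was implemented to determine the source of the difference in group comparisons". It does not give the number of comparisons or the error term. The section also names Mann-Whitney U for two-group comparisons, and Friedman with Wilcoxon follow-ups for within-group comparisons of non-normal data. It mentions no homogeneity-of-variance check, Welch-type test or transformation. The documents give no expected mean or SD for CFU.

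**The concern.** Ordinary one-way ANOVA assumes a common SD as well as normality. The spread of colony counts commonly rises with their mean, so an arm that is scrubbed more effectively may also have a smaller SD. Passing a normality check in each arm does not rule that out.

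The overall F test tolerates this fairly well when arms are equal in size. Pairwise follow-ups with a pooled error do not, because each pair is judged against an SD averaged over all four arms, two of which are not being compared. If 2 minutes lowers mean and spread, Groups I and II are the noisier pair and III and IV the quieter one. The pooled SD lies between the two. The brush question at 2 minutes is then tested too conservatively and the one at 1 minute too liberally. Both bear on the method hypothesis, and a real brush effect at 2 minutes could be missed.

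**Working it through.** **The plan's own figure.** With 4 groups, f = 0.25, alpha 0.05 and N = 180, the noncentrality is 180 × 0.25² = 11.25 on (3, 176) degrees of freedom. Power is 0.804. The smallest N divisible by 4 that reaches 0.80 is 180, so the stated figure reproduces, and it is a figure for ordinary ANOVA.

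**Inputs.**
- From the documents: 4 arms, 45 per arm, Bonferroni correction.
- Assumed: all 6 pairs compared, so 0.05/6 = 0.0083 each; pooled ANOVA error; normal data; SDs r, r, 1, 1 for Groups I to IV, with r from 1 to 3; a true III v IV difference of 0.8 of the 2-minute SD.

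**Formulas.**
- Pooled variance = (r² + r² + 1 + 1)/4 = (r² + 1)/2.
- Pooled SE of any pair = √(2 × pooled variance/45).
- True SE = r√(2/45) for I v II, and √(2/45) = 0.211 for III v IV.
- Critical t at 0.0083 two-sided on 176 df = 2.668.
- Power for III v IV ≈ P(Z > (2.668 × pooled SE − 0.8)/0.211).
- Error for I v II ≈ 2P(Z > 2.668 × pooled SE/true SE).

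**Worked case, r = 2.** Pooled variance = 10/4 = 2.5 and pooled SE = √(5/45) = 0.333. The smallest difference declared significant is 2.668 × 0.333 = 0.889. Power for III v IV = P(Z > (0.889 − 0.8)/0.211) = P(Z > 0.42) = 0.34. For I v II the true SE is 2 × 0.211 = 0.422, so the effective cut-off is 0.889/0.422 = 2.11 and the error rate is 0.035.

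| SD ratio r | Pooled variance | Pooled SE | Critical difference | Power, III v IV | Error, I v II |
|---|---|---|---|---|---|
| 1 | 1.00 | 0.211 | 0.563 | 0.87 | 0.008 |
| 1.25 | 1.28 | 0.239 | 0.637 | 0.78 | 0.016 |
| 1.5 | 1.625 | 0.269 | 0.717 | 0.65 | 0.023 |
| 2 | 2.50 | 0.333 | 0.889 | 0.34 | 0.035 |
| 3 | 5.00 | 0.471 | 1.258 | 0.01 to 0.02 | 0.047 |

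With a Welch t test on the two arms alone, the critical t on about 88 df is 2.699, the critical difference is 2.699 × 0.211 = 0.569, and power is P(Z > (0.569 − 0.8)/0.211) = 0.86 at every r.

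**Simulation.** Normal-data simulations of 20,000 to 40,000 trials per case agree. At r = 1.5 the I v II error is about 0.025 and III v IV power 0.65. At r = 2 they are 0.035 to 0.038 and 0.34 to 0.35. Welch keeps the I v II error at 0.007 to 0.009 and power at 0.86. The overall F test, with equal means and r from 1.5 to 3, rejects in 0.057 to 0.068 of trials, close to nominal.

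**How often the ANOVA route is taken.** The figures above send every trial to ANOVA. Over-dispersed counts (means 200, 200, 100, 100, SD proportional to the mean) were therefore passed through a Lilliefors-corrected Kolmogorov-Smirnov test in each arm. All four arms passed in about 50% of trials at a coefficient of variation (CV) of 0.3, 17% at 0.5, and almost none at 0.7 or more. Without the correction all four passed in 99% at CV 0.3, 95% at 0.5 and 24% at 1.0. If all 180 values are tested together, the Lilliefors test almost never passes. The plan does not say which version is used or on which values.

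**The case against.** The strongest reply is that the harm needs three things together, none of which the documents establish: CFU passes the normality check, the follow-ups use the pooled error, and the SDs differ. This stands, and the point is worded conditionally for that reason.

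- **CFU may have gone the rank route.** It is the only outcome the Data Collection section describes as sampled repeatedly, and the only within-group tests named are Friedman and Wilcoxon, for non-normal data. That hints, without proving, that CFU was treated as non-normal. Against this, the trial was sized for ANOVA.
- **The error term is unstated.** Bonferroni-adjusted separate two-arm tests would not have the fault. Pooled error is the natural reading when Bonferroni directly follows ANOVA, but it is a reading.
- **False positives.** A reader might infer that the plan would usually report a spurious brush effect at 1 minute. It would not. Even at r = 2 with every trial sent to ANOVA, about 96% of trials with no brush effect report nothing there. With the normality check applied and Mann-Whitney otherwise, the simulated rate was 0.025 at CV 0.3 and 0.007 to 0.013 at CV 0.4 to 1.0.
- **The rank branch.** A reader might extend the criticism to Kruskal-Wallis follow-ups based on joint four-arm ranks. The documents describe no such procedure, and they name Mann-Whitney U for two-group comparisons.
- **Scale.** If SD is proportional to the mean, a log scale would roughly equalise the SDs. True, but the plan names no transformation.
- **Simplification.** The power runs give III and IV the same SD although their means differ, so those figures are approximate.

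**Conclusion.** The concern holds in conditional form. The omission is plain in the text: normality alone admits a variable to equal-variance ANOVA. If CFU takes that route with pooled follow-ups and time reduces its spread, power for a 0.8-SD brush effect at 2 minutes falls from 0.86 to about 0.65 (SD ratio 1.5) or 0.35 (ratio 2). The 1-minute error is roughly three to four times its 0.0083 level, but by itself stays below 5% at those ratios. It reaches about 5% at ratio 3 and about 6% in the limit.

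The SD ratios, six comparisons and pooled error are assumptions. There is no problem if SDs are equal, or if CFU goes to Kruskal-Wallis with two-arm Mann-Whitney follow-ups. Because the normality check diverts many skewed data sets from ANOVA, the effect over all trials is smaller than these figures. The documents do not support the inference that the trial's brush results are wrong.

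**What to change.** In the Statistical Analysis section, replace one-way ANOVA with Welch's ANOVA. Replace its Bonferroni follow-ups with Games-Howell, or with Welch t tests on the two arms compared under the plan's own Bonferroni correction. In the same sentence, state the number of comparisons and that each uses only its own two arms' variances.

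This takes two sentences, standard software and no new data. If SDs are in fact equal, overall power at f = 0.25 and N = 180 goes from about 0.803 to 0.797, and pairwise power from 0.868 to 0.859 with Welch t tests. Games-Howell showed no loss (0.88).
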